
Recorded data age, BMI, type, site and duration of surgery, type of lymphadenectomy (radical vs regional/sentinel lymph node), intraoperative fentanyl (µg), postoperative morphine (mg), and time-to-opioid first rescue dose. First 24 hours' total opioid requirements (intraoperative+postoperative, primary outcome) were calculated by converting fentanyl used intraoperatively into morphine equivalents (fentanyl conversion factor; 10 µg fentanyl=1 mg morphine). The participants are blinded to group allocation, as the blocks were performed after induction of general anesthesia. The healthcare provider (attending anesthesiologist) who administer the opioid was blinded to subject allocation as he is not present in the operating room during the standard time used by the investigator to perform the block, even for control subjects who do not receive any block. When attending anesthesiologist is called back to the operating room, the same equipment was present (US machine and disposable items needed to perform the technique, such as syringes and vials) and a white dressing that prevented injection identification is placed on all subjects. In the postoperative period, pain is

assessed by the VAS at 1, 3, 6, 12, and 24 hours after surgery. The occurrence of side effects (nausea, pruritus, apnea, urinary retention, or paralytic ileus), block-related complications, and Pain Out questionnaire answers is recorded at 24 hours after surgery. The data collector for the postoperative data is a different investigator from the one who performed the block and was blinded to the subjects' study group allocation.

The study has planned data monitoring and auditing by the IIS la Fe according to AEMPS guidelines. Consistency will be checked during analysis phase with Stata statistical software. Registries will be obtained from electronic medical records available for double check procedures. All variables are obtained from the subject electronic medical record.

Sample size: Considering a decrease in postoperative morphine consumption of 40% and the average consumption of opioid after breast surgery under general anesthesia is 15 milligrams (standard deviation 8 mg) we calculated that , with an alpha error 5% power 80 % 56 patients (28 per group) were required to achieve a significant result. In anticipation of possible loss of sample , 60 patients were recruited . Analysis will be performed by intention to treat.

Statistical Analysis Plan

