Continuous variables were reported as medians with IQRs or means with SDs where applicable; categorical variables were reported as counts and percentages. We checked for the normality of continuous variables by using the Shapiro-Wilk test.

Quantitative variables (opioid consumption , pain estimated by VAS scale) will be analyzed using mixed linear model adding a random variable for interindividual variability for pain threshold. If the data do not meet the criteria of normality the Mann-Whitney U test will be used. If the groups differ in preoperative variables., We will make a multivariable analysis adjusting for these variables. The need for rescue analgesia over time is analyzed by Kaplan-Meier curve where the terminal state is the administration of the first dose of opioid postoperatively. The difference side effects (nausea , pruritus , apnea , urinary retention, ileus) and complications IPO questionnaire and analyzed by chi-square test and Fisher exact test. Scheffe correction will be applied for multiple comparison. Missing data are excluded from analysis.

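### Chi-square and Fisher tests for the Pain Out questionnaire would discard the order of any graded items, at a material cost in power; yes/no items and VAS pain are unaffected

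*Combined protocol and SAP*

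**What the plan says.** In the Methods, the paragraph on postoperative assessments says that side effects, block-related complications "and Pain Out questionnaire answers is recorded at 24 hours after surgery". It gives no list of items, no response scales and no cut-points. The same paragraph has pain "assessed by the VAS at 1, 3, 6, 12, and 24 hours after surgery".

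The Statistical Analysis Plan then divides the outcomes in two:

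- "Quantitative variables (opioid consumption , pain estimated by VAS scale) will be analyzed using mixed linear model", followed by "If the data do not meet the criteria of normality the Mann-Whitney U test will be used".
- Side effects and "complications IPO questionnaire and analyzed by chi-square test and Fisher exact test".

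The second sentence is grammatically broken, and IPO is not defined. Pain Out is the only questionnaire named in the document, and the Methods list the same three things together (side effects, complications, questionnaire). Reading IPO as Pain Out is therefore a sound inference, though the document does not state it. No other sentence assigns the questionnaire a method.

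**The concern.** On a table of two arms by k answer levels, Pearson's chi-square and the Fisher-type exact test give the same p-value however the columns are shuffled. That is right for unordered categories and harmless for two levels. On a graded item, though, a consistent move towards the better answers is the effect of interest, and these tests cannot distinguish it from any other pattern of differences. The evidence is spread over k − 1 degrees of freedom instead of being concentrated on one.

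At stake is the reading of a secondary patient-reported outcome. For graded items, a non-significant result would say less than it appears to, and the p-value would come with no estimate of the size or direction of the shift. The primary outcome, 24-hour opioid requirement, is not touched.

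**Working it through.** **Inputs from the document**

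- Sample size paragraph: "Considering a decrease in postoperative morphine consumption of 40" per cent, from a mean of 15 mg with SD 8 mg; "with an alpha error 5% power 80 % 56 patients (28 per group) were required"; 60 recruited.
- Methods: 1:1 allocation, so about 30 per arm.

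**Step 1. Reproduce the plan's own figure.**

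Difference = 0.40 × 15 = 6 mg. Standardised effect = 6/8 = 0.75.

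n per group = 2 × (1.960 + 0.842)² / 0.75² = 27.9, rounded up to 28.

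Power at 28 per group = Φ(0.75 × √(28/2) − 1.960) = Φ(0.846) = 80.1%.

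The stated 28 per group is reproduced with a two-sided 5% test. The document does not state the sidedness; a one-sided test would give 22.

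**Step 2. What order-blind testing does to a graded item.**

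Degrees of freedom are (2 − 1)(k − 1): 10 for 11 levels, 4 for 5, 3 for 4 and 1 for a yes/no item. Thirty patients in an arm average 30/11 = 2.7 per cell with 11 levels, 6 with 5 and 7.5 with 4.

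**Step 3. Power by simulation.**

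Assumptions, none of them from the document except the arm size and the 5% level:

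- a normal latent answer, shifted between arms and cut into k ordered levels (equal-width cuts over ±2 SD; mid-point cut for k = 2);
- 30 per arm, two-sided 5%, no multiplicity adjustment;
- 4,000 simulated trials per case (2,000 for the exact test on graded items).

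| Levels | Shift (SD) | Chi-square | Fisher-type exact | Mann–Whitney |
|---|---|---|---|---|
| 11 | 0.5 | 11% | 15% | 45% |
| 11 | 0.75 | 29% | 33% | 79% |
| 11 | 1.0 | 54% | 60% | 96% |
| 5 | 0.5 | 20% | 25% | 42% |
| 5 | 0.75 | 47% | 53% | 74% |
| 5 | 1.0 | 76% | 81% | 93% |
| 4 | 0.5 | 21% | 26% | 36% |
| 4 | 0.75 | 45% | 55% | 67% |
| 4 | 1.0 | 75% | 81% | 89% |
| 2 (yes/no) | 0.75 | 65% | 53% | 65% |

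**Step 4. Is the gap an artefact of test size?**

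With no true shift, rejection on graded items was 2.4–3.5% for chi-square, 3–5% for the exact test and about 5% for Mann–Whitney. Conservatism of chi-square therefore explains part of its deficit, but not most of it. The exact test rejected 4.9% (5 levels) and 4.3% (11 levels) under the null, and at 0.75 SD it still reached only 53% and 33%, against 74% and 79%.

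**Step 5. Sensitivity.**

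- Cut placement. Further simulations with other placements of the levels gave, at 0.75 SD, chi-square against rank test: 30–32% against 78–79% (11 levels), 50–55% against 76–78% (5 levels) and 56–59% against 75–77% (4 levels). Pooling all runs and both unordered tests:
  - 0.75 SD: 29–34% against 78–79% (11 levels), and 45–59% against 67–78% (4–5 levels);
  - 0.5 SD, 4 to 11 levels: 11–29% against 36–46%;
  - 1.0 SD, 4 to 11 levels: 54–85% against 89–96%.
- Arm size. At 28 per arm and 0.75 SD, chi-square against Mann–Whitney is 25.1% against 76.5% (11 levels), 43.5% against 71.5% (5) and 44.4% against 65.0% (4).
- Collapsing to two categories. A mid-scale split at 0.75 SD and 30 per arm gives 61%, 55% and 63% by chi-square (11, 5 and 4 levels) and 51%, 44% and 52% by Fisher. This stays below the rank test, and the plan names no cut-point.

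**The case against.** The strongest objection is that nothing in the document says any questionnaire item is graded. If all items are yes/no, the planned tests are appropriate. This stands, and it makes the point conditional. It does not remove it: the plan fixes one pair of tests for the whole questionnaire without saying what kind of data it yields, and the proposed wording is safe either way.

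A reader might infer that the trial is likely to miss a real shift in patient-reported pain. The document does not support that. Pain is also scored by VAS at five times, one of them at the questionnaire's own 24-hour time point, and goes to a mixed linear model or Mann–Whitney, both of which use order. Nor does the document show that the questionnaire is the trial's main record of pain; it is mentioned once as a 24-hour recording.

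A reader might also infer that a false negative is the likely result for every graded item. That depends on the assumptions. It holds for 11 levels at 0.75 SD, and for every graded case at 0.5 SD, where the rank test is also below 50%. With 4 or 5 levels at 0.75 SD the unordered tests are close to even odds. At 1.0 SD they detect the shift more often than not.

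The 0.75 SD shift belongs to morphine consumption. Both arms have a PCA pump and are told to use it when VAS reaches 40 mm, which may narrow differences in pain while opioid use differs. The shift serves only as a yardstick. The power figures also ignore the multiple-comparison correction that the plan mentions.

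Finally, the general rule for quantitative variables could be read to cover numeric questionnaire items. Its parenthesis names only opioid consumption and VAS, and the questionnaire is placed explicitly elsewhere, so the plan as written does not lead there.

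**Conclusion.** The point holds in conditional form. As written, the plan analyses the questionnaire with tests that ignore order. For any graded or numeric item this costs roughly 45 to 50 percentage points of power with 11 levels and roughly 12 to 27 points with 4 or 5 levels, at 30 per arm and 0.75 SD. Level counts, cut placement and shift sizes are assumptions. The direction of the loss is not sensitive to them: the rank test was ahead in every graded case examined.

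Severity is low, because the questionnaire is not the primary outcome, was not used for sizing, and pain has an order-respecting analysis through VAS. Confidence is moderate: the item scales are unstated, and the identity of IPO with Pain Out is inferred.

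**What to change.** State which questionnaire items are yes/no and which are graded or numeric, use one name for the questionnaire throughout, and replace the sentence along these lines:

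> Side effects, complications and yes/no items of the Pain Out questionnaire will be compared by chi-square or Fisher's exact test. Graded or numeric items will be compared by the Wilcoxon–Mann–Whitney test and reported with the Hodges–Lehmann shift and its 95% confidence interval.

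For items with few levels, a common odds ratio with 95% CI from a proportional-odds model is a reasonable alternative. The rank test is already the plan's fallback for opioid use and VAS, so no new method is needed. The cost is one sentence and a short item list, with no new data and no extra patients. The change should be dated before the questionnaire data are compared by arm.

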Healthcare, Chicago, Illinois, USA), bispectral index module (BIS module, GE Healthcare, Helsinki, Finland), and TOF-Watch-S (Organon Teknika, Oss, The Netherlands), general anesthesia is induced with intravenous midazolam 0.01–0.03 mg/kg, fentanyl 1 µg/kg, and propofol 2 mg/kg. A laryngeal mask is introduced after the administration of intravenous rocuronium bromide 0.6 mg/kg for muscle relaxation. The lungs are ventilated to maintain an end-tidal carbon dioxide of 35 mm Hg. Anesthesia is maintained with an oxygen fraction (FiO₂) of 0.4 and propofol continuous intravenous infusion to keep BIS index between 40 and 60. After anesthesia induction, patients are randomly allocated into two groups (1:1 allocation ratio) by a random sequence generated from a pseudorandom number seed (!RNDSEQ V.2011.09.0, JMDomenech); these sequences is kept in sealed and consecutively numbered opaque envelopes, which are opened after informed consent is obtained. Patients in the study group receive SPB with the midaxillary line approach, using levobupivacaine 0.25% 30 mL, while those in the control group do not. An anesthetist with experience in interfascial blocks perform the US-guided technique using a linear probe (8–13 MHz), a US machine (M-Turbo, SonoSite, Bothell, Washington, USA), and a 22 G, 50 mm echogenic needle (Stimuplex D; B Braun, Melsungen, Germany). With the patient lying supine and the arm abducted at 90°, the US probe is positioned in a sagittal plane at the midaxillary line. The fascial plane between the serratus anterior muscle and external intercostal muscles is identified between the fourth and fifth ribs in the midaxillary region. The gauge is advanced in-plane, and the local anesthetic is placed by hydrodissecting the interfascial space in a caudal to cranial fashion. Following the initial bolus of fentanyl during induction, perioperative analgesia is achieved by administering a bolus of 1 µg/kg fentanyl if blood pressure and/or heart rate increased $\geq 20\%$ from baseline measurement (first operating room assessment). Thirty minutes before the end of surgery, intravenous paracetamol 1 g is administered in both groups. At the end of surgery, intravenous granisetron 40 µg/kg and dexamethasone 4 mg is administered; muscle relaxation is reversed if needed. During the postoperative period, all patients receive intravenous opioid medication on demand via an electronic PCA pump (CADD Solis, Smiths Medical, Minneapolis, Minnesota, USA). The pump is set to deliver a bolus dose of 1 mg, with a lockout interval of 10 min, and maximum dose of 6 mg/hour without continuous perfusion. The patient is instructed to press the PCA button whenever pain increased to VAS ≥ 40 mm. Moreover, intravenous paracetamol 1 g/8 hours and dexketoprofen 50 mg/8 hours is administered in both groups, as part of multimodal analgesia management.

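### Complications are put to a between-arm test although the only ones recorded are block-related and controls receive no block, so the p-value tells the reader almost nothing

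*Combined protocol and SAP*

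**What the plan says.** The Methods paragraph on recorded data lists five side effects, then "block-related complications, and Pain Out questionnaire answers is recorded at 24 hours after surgery". No other category of complication is named.

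The Statistical Analysis Plan takes the same items in the same order (side effects, complications, questionnaire) and assigns them to tests of a difference: "complications IPO questionnaire and analyzed by chi-square test and Fisher exact test". The sentence has lost some words and does not repeat that the complications are block-related. It gives no rule for choosing between the two tests. Elsewhere the plan says that categorical variables are given as counts and percentages; it mentions no confidence interval.

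On exposure, the Methods state that the study group receives the block "using levobupivacaine 0.25% 30 mL, while those in the control group do not". The blinding procedure matches waiting time, equipment and dressing, "even for control subjects who do not receive any block". No sham injection is described.

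**The concern.** If an event counts as a complication only because the block caused it, a patient who had no block cannot have it. Whether the arms differ is then settled by the first such event, and the only open question is how often it happens in patients who receive the block. A between-arm test does not answer that. In a trial of this size, the likely result at low complication rates is a non-significant p-value, printed beside a count that may be clinically relevant. For example, 3/30 against 0/30 would be reported as no significant difference. The block-arm rate and its uncertainty, which the trial can estimate, would not be given an interval.

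**Working it through.** **Inputs**
- Allocation: "patients are randomly allocated into two groups (1:1 allocation ratio" (Methods).
- Size: "with an alpha error 5% power 80 % 56 patients (28 per group) were required" (Sample size), with 60 recruited, so 30 per arm.
- Control-arm block-related events: 0, because no block or sham is given.
- Block-arm complication rate: not in the documents. 5%, 10% and 15% are assumed below.

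**The plan's own figure.** The sample size rests on "the average consumption of opioid after breast surgery under general anesthesia is 15 milligrams (standard deviation 8 mg" and a 40% reduction, that is 0.40 × 15 = 6 mg. With two-sided alpha 5% (sidedness is not stated) and 80% power:

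n per arm = 2 × (1.960 + 0.842)² × 8² / 6² = 2 × 7.85 × 1.778 ≈ 27.9, rounded up to 28, total 56.

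This reproduces. It concerns opioid consumption only; no size or power is stated for complications.

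**Fisher exact test, k/30 against 0/30.** With equal arms and no control events, the two-sided p-value is 2 × C(30,k) / C(60,k).
- k = 3: 2 × 4,060 / 34,220 = 0.24
- k = 4: 2 × 27,405 / 487,635 = 0.11
- k = 5: 2 × 142,506 / 5,461,512 = 0.052
- k = 6: 2 × 593,775 / 50,063,860 = 0.024

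Significance therefore needs at least 6/30, or 20%. With 28 per arm it also needs 6 (5/28 gives 0.0515, 6/28 gives 0.023).

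**Uncorrected chi-square.** The statistic is 60 × (30k)² / (30 × 30 × k × (60 − k)).
- k = 3: 3.16, p = 0.076
- k = 4: 4.29, p = 0.038
- k = 5: 5.45, p = 0.020

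This test crosses 5% at 4/30. At 4 or 5 events the two named tests disagree, and the plan does not say which applies.

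**Chance of a significant result, 30 per arm.** P(X ≥ c), with X binomial (30, true rate), c = 6 for Fisher and c = 4 for uncorrected chi-square:

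| Assumed true rate | Fisher | Uncorrected chi-square |
|---|---|---|
| 5% | 0.3% | 6.1% |
| 10% | 7.3% | 35.3% |
| 15% | 28.9% | 67.8% |

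**What the block arm alone can say.** Clopper-Pearson 95% limits:
- 0/30: upper limit 1 − 0.025^(1/30) = 11.6% (0/28: 12.3%)
- 1/30: 0.1% to 17.2%
- 3/30: 2.1% to 26.5%

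So 3/30 yields p = 0.24 from the planned Fisher test, while the interval shows data compatible with a rate of about one in four.

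**The case against.** Several counter-arguments have force.

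- **The sentence is garbled.** The plan never writes that block-related complications are tested; that comes from reading it with the Methods. The reading is well supported, because the Methods name no other complications and the order of items matches, but it remains an inference.
- **A zero in controls is expected, not guaranteed.** A reader might infer that the control count is zero by design and the null hypothesis therefore meaningless. The documents do not support that in full. Postoperative data are collected by an investigator blinded to allocation, the dressing hides any injection site, and qualifying events are not listed. A haematoma after surgery could be recorded as block-related in a control. Comparing all such look-alike events between arms would not be invalid, though at this size it would have little power.
- **No safety claim is planned.** A reader might infer that a non-significant result will be presented as evidence of safety. Nothing in the documents says so; the stated purpose is analgesic efficacy. The background's remark on safety contrasts newer techniques with paravertebral block, which is not an arm of this trial, so neither the planned test nor an interval would bear on it.
- **Raw counts will be visible.** The plan does provide for counts and percentages, so the p-value would not stand alone.

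These points limit the concern to what one p-value can convey. They do not make that p-value informative for events attributable to the block.

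**Conclusion.** The point stands as a minor one. As written, the plan tests complications between arms when the only recorded complications belong to a procedure that one arm does not undergo. For truly block-related events, Fisher can be significant only at 6/30 or more and uncorrected chi-square only at 4/30 or more, so at low rates non-significance is the likely result whatever the block does.

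This rests on reading complications in the Statistical Analysis Plan as the block-related ones in the Methods, on no control events, and on 30 analysed per arm. The 5%, 10% and 15% rates are assumptions. The primary outcome is unaffected.

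**What to change.** Amend the sentence in the Statistical Analysis Plan so that:

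1. Block-related complications are taken out of the hypothesis tests.
2. They are reported descriptively as counts and percentages in each arm, keeping any event that the blinded collector records in a control.
3. The block-arm percentage carries an exact (Clopper-Pearson) 95% confidence interval.
4. Chi-square or Fisher tests are kept for nausea, pruritus, apnea, urinary retention and ileus, which can occur in either arm.

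The cost is one rewritten sentence and one lost p-value. No new data are needed. Reporting both arms, rather than the block arm alone, avoids discarding control events and avoids having to attribute events after unblinding.

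### The Scheffé correction does not suit this two-arm trial's secondary tests: time by time it corrects nothing, over five VAS contrasts it is needlessly strict, and it gives no joint threshold for the rank and categorical tests

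*Combined protocol and SAP*

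**What the plan says.** The Methods describe two arms allocated 1:1 and one primary outcome, total opioid requirement over the first 24 hours. Pain is "assessed by the VAS at 1, 3, 6, 12, and 24 hours after surgery". For the categorical outcomes, "The occurrence of side effects (nausea, pruritus, apnea, urinary retention, or paralytic ileus), block-related complications, and Pain Out questionnaire answers is recorded" at 24 hours.

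The Statistical Analysis Plan says that opioid consumption and VAS "will be analyzed using mixed linear model adding a random variable for interindividual variability for pain threshold". It adds a fallback: "If the data do not meet the criteria of normality the Mann-Whitney U test will be used". Side effects, complications and the questionnaire are "analyzed by chi-square test and Fisher exact test". For time to first rescue opioid, "The need for rescue analgesia over time is analyzed by Kaplan-Meier curve".

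One sentence then covers multiplicity: "Scheffe correction will be applied for multiple comparison". It gives no family, no contrast space and no error degrees of freedom. It does not say how the rule carries over to the rank and categorical tests. It directly follows the sentence on side effects, complications and the questionnaire.

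**The concern.** Scheffé's method protects all linear contrasts among means in a model with a common error variance. It is most useful when there are several groups and the contrasts are not fixed in advance. Here there are two groups, so at any one time there is only one contrast between them. The multiplicity comes from repeated times and from different events, and the sentence does not say how Scheffé is to deal with either.

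For VAS, the same data could be judged at |t| > 2.00 or at |t| > 3.45, and either could be reported as a Scheffé analysis. A time point with p = 0.02 or p = 0.005 would be significant under one reading and not under the other, and the choice could be made after the data are seen. For VAS under the rank fallback, and for the categorical outcomes, the promised correction has no working form.

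**Working it through.** **Inputs from the documents.** Two arms; 28 per arm required and 60 patients recruited (30 per arm); five VAS times; five named side effects; alpha 5%. Sidedness is not stated, but two-sided reproduces the stated sample size.

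**Assumptions (the documents give no figures).** VAS effect of 0.5 to 1.0 SD; correlation between VAS times of 0.3 to 0.7; side-effect rates as shown below; Fisher when any expected count is below 5, otherwise uncorrected chi-square.

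**The plan's own figure.** The difference is 40% of 15 mg = 6 mg, with SD 8 mg. n per arm = 2 × [(1.960 + 0.842) × 8/6]² = 27.9, so 28 per arm and 56 in total. This reproduces and does not depend on the Scheffé rule.

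**Critical values.** Scheffé over a contrast space of rank r: √(r × F(0.95; r, df)). With 30 per arm, df = 58:

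- Unadjusted: t(0.975; 58) = 2.002.
- Scheffé, one time (r = 1): √(1 × 4.007) = 2.002, the same value.
- Bonferroni over five tests, which is also Holm's strictest step: t(0.995; 58) = 2.663, per-test p = 0.01.
- Scheffé, five contrasts (r = 5): √(5 × 2.374) = 3.445, per-test p = 0.0011.

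With 28 per arm (54 df) the four values are 2.005, 2.005, 2.670 and 3.454. Other contrast spaces at 58 df give 3.18 (r = 4, interaction contrasts only) and 4.29 (r = 9, all contrasts among the ten arm-by-time means). With r = 5 and 290 df (60 × 5 observations less 10 cell means), Scheffé is 3.350 against 2.593 for Bonferroni. Scheffé is the stricter in every case.

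**Family-wise error over five VAS times** (40,000 simulated null trials, 30 per arm):

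| Correlation | Unadjusted, or Scheffé time by time | Holm | Scheffé, r = 5 |
|---|---|---|---|
| 0.3 | 21.2% | 4.7% | 0.53% |
| 0.5 | 18.4% | 4.3% | 0.50% |
| 0.7 | 15.1% | 3.6% | 0.44% |

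An equicorrelated normal integral gives 20.9%, 18.3% and 14.8% for the unadjusted column. Independence would give 1 − 0.95⁵ = 22.6%.

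**Power at one VAS time** (noncentral t, 30 per arm, noncentrality = d × √(30/2)):

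| Assumed effect d | Noncentrality | Bonferroni | Scheffé, r = 5 |
|---|---|---|---|
| 0.5 SD | 1.936 | 24% | 8% |
| 0.75 SD | 2.905 | 60% | 31% |
| 1.0 SD | 3.873 | 88% | 66% |

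Holm is at least as powerful as Bonferroni, so these gaps are lower bounds for Holm against Scheffé.

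**Rank and categorical tests.** Scheffé supplies no joint threshold across Mann-Whitney tests at different times, or across chi-square or Fisher tests on different events. Large-sample analogues exist for ranks and proportions across several groups. With two groups they have 1 df and again correct nothing.

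**Side effects left unadjusted** (exact enumeration, 30 per arm, five independent tests, 1 − (1 − size)⁵ from unrounded sizes):

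- All rates 5%: size 0.15% per test, family 0.8%.
- All rates 10%: size 1.2%, family 6.0%.
- All rates 25%: size 4.8%, family 21.8%.
- All rates 50%: size 5.2%, family 23.4%.
- One rate 30% and four at 5%: family 5.4%.

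**The case against.** The strongest reply is that the time-by-time reading is the least natural one. The sentence speaks of multiple comparisons, and the planned VAS analysis is a single mixed model with a patient-level random term. Scheffé over contrasts in that model is legitimate and does not inflate error. That stands: 15-21% is the error under one of the readings left open, not the error of the plan. A reader might infer that VAS error is certainly uncontrolled, and the documents do not support that.

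The plan also never says that the arms will be compared at each time. A mixed model can give one overall arm effect, and then VAS has no multiplicity to correct. That stands too, so the fix for VAS is conditional.

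The documents give no VAS effect, so the size of the power loss is unknown. It is shown over a range for that reason. With a smaller contrast space the loss shrinks: r = 4 gives 40% rather than 31% at 0.75 SD. The direction does not change.

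For side effects, a reader might infer error above 20%. That needs all five events, apnea and ileus among them, at rates of about 25-50%. When events are rare, the discreteness of Fisher's test already keeps the error low. Adjusting harms also makes them harder to flag. Both points stand. They limit the practical harm, but they do not give the stated correction a usable form.

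**Conclusion.** The point holds for secondary outcomes. Depending on a choice the plan leaves open, its multiplicity rule either changes nothing for VAS or holds family-wise error near 0.5% when 5% would do, at a real cost in power. For separate rank and categorical tests it cannot be carried out as a joint correction.

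The equality at one contrast is exact, and the critical values follow from the design and the df used. The family-wise error rates rest on assumed correlations, the power figures on assumed VAS effects, and the side-effect figures on assumed event rates, independence and a Fisher rule.

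A reader might go further and infer that the main result or the sample size is compromised. The documents do not support this: there is a single primary outcome, and the 56-patient calculation does not involve Scheffé. The sentence does not confine itself to secondary tests. Reading it that way is an inference, but a reasonable one with one primary outcome. The change should be made, and it is one of wording.

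**What to change.** Replace the Scheffé sentence with:

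> The primary outcome is tested alone at two-sided 5%. If the arms are compared at each VAS time (1, 3, 6, 12, 24 h), the five mixed-model contrasts, or the five Mann-Whitney tests under the fallback, form one family with Holm-adjusted p-values. The chi-square/Fisher tests of side effects, complications and questionnaire answers use Holm-adjusted p-values within each of these three sets. All other secondary comparisons, including time to first rescue opioid and the separate intraoperative and postoperative opioid amounts, are reported as secondary without multiplicity adjustment.

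Holm works on p-values, so one rule serves the model, rank and exact tests. Complications and questionnaire answers keep a correction, since the sentence just before the Scheffé rule covers them.

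The cost is SAP wording only; the primary analysis and the sample size stay as they are. Adjusted secondary p-values, including those for harms, become somewhat less favourable than with no correction, so unadjusted counts and percentages for harms should still be shown. Against five-contrast Scheffé, VAS power rises. With very common events tested by uncorrected chi-square, Holm can run slightly above 5%: 6.6% if all five side-effect rates were 50%.
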